ICH	International Council for Harmonisation
IMO	Immune Modulatory Oligonucleotide
irAE	Immune-related adverse event
irRC	Immune-related response criteria
irRECIST	Immune-related reponse evaluation criteria solid tumors
ISR	Injection site reaction
LFT	Liver function test
MLE	Maximum Least-square Estimation
MTD	Maximum tolerated dose
NCI	National Cancer Institute
ORR	Objective response rate
OS	Overall survival
PD	Progressive disease
PFS	Progression-free survival
PI	Principal Investigator
PK	Pharmacokinetic
PR	Partial response
Pr	Probability
PRO	Patient reported outcome
PT	Prothrombin time
RBC	Red blood cell
RP2D	Recommended Phase 2 dose

SAE	Serious adverse event
SD	Stable disease
ULN	Upper limit of normal
WBC	White blood cell

DEFINITIONS

Adverse Event	An adverse event (AE) is any reaction, side effect, or other untoward event, regardless of relationship to study drug, which occurs anytime during the study.
DLT Evaluable Population	All subjects in the Safety Population who continue participation in the study for the entire DLT evaluation period, or who discontinue prematurely due to a DLT.
DLT Evaluation Period	The DLT evaluation period will be Cycle 1 (Weeks 1 through 4).
Safety Population	All subjects who received at least one dose of IMO-2125.
Serious AE	An AE occurring at any dose that: results in death; is a life-threatening experience; requires hospitalization or prolongation of an existing hospitalization; results in a persistent or significant disability/incapacity; or is a congenital anomaly/birth defect in the offspring of a subject who received study drug; or important medical event that, although not immediately life-threatening, requires intervention in order to prevent one of the listed serious outcomes listed.
Study Drug	IMO-2125 in combination with ipilimumab or pembrolizumab
Treatment-emergent AE	AEs with an onset date on or after the date of the initial dose of study drug, or an AE that worsens after the date of the initial dose of study drug.

1. INTRODUCTION

This document outlines the statistical methods to be implemented during the analyses of data collected within the scope of Idera Protocol Number: 2125-204 [A Phase 1/2 Study to Assess the Safety and Efficacy of Intratumoral IMO-2125 in Combination with Ipilimumab or Pembrolizumab in Subjects with Metastatic Melanoma]. The purpose of this plan is to provide specific guidelines from which the statistical analyses will proceed. Any deviations from this plan will be documented in the clinical study report (CSR).

2. STUDY OBJECTIVES

2.1 Primary Objective

The primary objective of Phase 1 is to characterize the safety and determine a recommended Phase 2 dose (RP2D) of IMO-2125 when administered in combination with ipilimumab or when administered in combination with pembrolizumab in subjects with metastatic melanoma. The maximum tolerated dose (MTD) and RP2D for IMO-2125 may differ between the combination of IMO-2125 and ipilimumab and the combination of IMO-2125 and pembrolizumab.

The primary objective of Phase 2 is to assess preliminary clinical activity of IMO-2125 in combination with ipilimumab or in combination with pembrolizumab at the respective RP2D(s) in subjects with metastatic melanoma that is not responsive to PD-1 inhibitor therapy, using Response Evaluation Criteria in Solid Tumors v1.1.

2.2 Secondary Objectives

The secondary objectives of Phase 1 are to determine the plasma pharmacokinetics (PK) of single-dose IMO-2125 and repeat-dose IMO-2125 PK administered intratumorally in combination with ipilimumab and pembrolizumab. An additional secondary objective of Phase 1 is to describe any preliminary antitumor activity.

The secondary objectives of Phase 2 are to further assess the safety and tolerability of IMO-2125 in combination with ipilimumab or in combination with pembrolizumab in subjects with metastatic melanoma and to assess treatment response using RECIST v1.1 and irRECIST, overall survival (OS), OS at 6 months and 12 months, progression-free survival (PFS), PFS at 6 months and 12 months, durable response rate (DRR), duration of response (DoR), and disease control rate (DCR).

2.3 Exploratory Objectives

The exploratory objectives of Phase 1 and 2 are to assess patient reported quality of life outcomes, pre- and post-treatment blood biomarkers, pre- and post-treatment tumor biopsies for immunological assessment, and explore any potential association between these biomarker measures and antitumor activity. In addition, anti-IMO-2125, anti-ipilimumab, and anti-pembrolizumab antibody formation will be assessed.

3. STUDY DESIGN AND PLAN

3.1 Overview

This is a two arm open-label Phase 1/2 study to assess the safety, tolerability, PK, immunogenicity, and efficacy of IMO-2125 when administered in combination with ipilimumab or in combination with pembrolizumab. Subjects with metastatic melanoma who have experienced symptomatic or confirmed radiographic progression to their most recent treatment regimen (anti-PD-[L]1 alone or in combination) will be eligible. Prior BRAF or MEK inhibitor treatment is not required. The study will be conducted in two parts: a dose-escalation portion (Phase 1) to evaluate safety and tolerability of multiple dose levels and a Phase 2 portion to assess preliminary efficacy.

3.1.1 Phase 1

The Phase 1 portion of the study is will explore escalating dose levels of IMO-2125 (from 4 to 32 mg with de-escalation to 2 mg allowed for each IMO-2125 combination). For each cohort, IMO-2125 will be administered as a once-weekly intratumorally injection for 3 consecutive weeks in Cycle 1, followed by intratumorally injections on Weeks 5, 8, 11, 17, 23, and 29 (Day 1 of Cycles 2 through 7). Both ipilimumab and pembrolizumab will be administered as per the USPI every 3 weeks beginning Day 1 of Week 2. Continued dosing of pembrolizumab following the study treatment period is permitted at the discretion of the Investigator for subjects in the IMO-2125 + pembrolizumab treatment arm. The dosing schedule is summarized in Table 1.

Table 1: Schedule of Dosing for Phase 1 and Phase 2

	Cycle															
	1				2			3			4			5	6	7
Study week	1	2	3	4	5	6	7	8	9	10	11	12	13	17	23	29
IMO-2125 + ipilimumab																
IMO-2125	X	X	X	-	X	-	-	X	-	-	X	-	-	X	X	X
Ipilimumab	-	X	-	-	X	-	-	X	-	-	X	-	-	-	-	-
IMO-2125 + pembrolizumab																
IMO-2125	X	X	X	-	X	-	-	X	-	-	X	-	-	X	X	X
Pembrolizumab	-	X	-	-	X	-	-	X	-	-	X	X ¹				

Note: On weeks when the combinations are administered, administration of ipilimumab or pembrolizumab will be first, followed by IMO-2125. IMO-2125 administration must occur within a ±2 day window of the scheduled dosing day.

¹ For subjects in the IMO-2125 + pembrolizumab treatment arm, continued pembrolizumab dosing per the approved product label is permitted at the discretion of the Investigator

Subjects assigned to 11 weeks of IMO-2125 under previous versions of the protocol who have not yet reached the end of the Treatment Period may receive the Week 17, 23, and 29 injections at the discretion of the treating Investigator.

Each cohort will be monitored for the occurrence of DLTs. The DLT evaluation period will be Cycle 1 (Weeks 1 through 4). If a subject discontinues study participation before the DLT evaluation period is finished due to reasons other than experiencing a DLT, that subject must be replaced so that the cohort may be properly evaluated. More information about the review of DLTs and the escalation of dose levels between cohorts is provided in Section 3.1.3, Section 3.1.4, and Section 3.1.5.

There are 3 subjects planned per cohort. During Phase 1, the sponsor will assign subjects to a treatment arm (IMO-2125 + ipilimumab or IMO-2125 + pembrolizumab) by cohort.

After completing the DLT evaluations for all planned IMO-2125 doses in either combination, supplemental cohorts of up to 5 subjects each may be enrolled with either combination at doses up to and including the MTD. After completion of either Phase 1 treatment arm and determination of the RP2D for that arm, the Phase 2 portion for the

completed treatment arm may be initiated. It is not necessary for Phase 1 to be completed in both treatment arms before Phase 2 is started.

3.1.2 Phase 2

The Phase 2 portion of the study will assess preliminary efficacy, using investigator-assessed RECIST v1.1, of IMO-2125 + ipilimumab, IMO-2125 + pembrolizumab, and any additional combinations that are studied in Phase 1. The dose level of IMO-2125 to be administered for each treatment arm will be the RP2D for the combination, as determined in Phase 1. Phase 2 will enroll up to 60 subjects treated at the IMO-2125 + ipilimumab RP2D. This will include at least 21 subjects in the primary IMO-2125 + ipilimumab efficacy-evaluable population and up to 20 subjects in the secondary IMO-2125 + ipilimumab efficacy-evaluable population. In the IMO-2125 + pembrolizumab Phase 2 cohort, enrollment will continue until 21 subjects in the IMO-2125 + pembrolizumab efficacy-evaluable population have been treated at the IMO-2125 + pembrolizumab RP2D. Phase 1 subjects treated at the RP2D for either combination may contribute to these totals. A two-stage design will be used to test for clinically and statistically relevant clinical activity. A treatment arm will stop if an interim futility analysis shows there is insufficient evidence of a clinically relevant response rate after 10 subjects (Stage 1).

If a subject discontinues treatment before completing at least one efficacy evaluation for reasons other than toxicity, then that subject will be replaced with the replacement assigned to the same treatment arm and dose level as the subject who dropped out early.

Combination therapy in Phase 2 will continue using the same schedule as Phase 1 (see **Table 1**).

3.1.3 Dose Escalation and Stopping Rules

Up to five dose levels for IMO-2125 are initially planned (**Table 2**).

Table 2: Treatment Doses to be investigated

Dose Level	IMO-2125	Ipilimumab	Pembrolizumab
-1	2 mg	3 mg/kg	200 mg
+1	4 mg	3 mg/kg	200 mg
+2	8 mg	3 mg/kg	200 mg
+3	16 mg	3 mg/kg	200 mg
+4	32 mg	3 mg/kg	200 mg

In Phase 1, the study will enroll subjects in planned cohorts of 3, beginning at Dose Level +1 for the ipilimumab treatment arm and beginning at Dose Level +2 for the pembrolizumab treatment arm once safety of the IMO-2125 + ipilimumab combination has been established for that level.

Additionally, if, due to observed toxicity, it proves difficult to provide IMO-2125 for 3 consecutive weeks in Cycle 1, the decision may be taken by the CRC to add cohorts where alternative schedules of IMO-2125 administration will be explored.

The MTD will be determined from the assessment of DLTs during the first treatment cycle of each cohort (Section 3.1.5). Using a prior beta(1,1) distribution of the DLT rate δ_i for each dose level i , the MTD is defined as the highest dose level for which the mean of the posterior distribution of toxicity is closest to 25% among all the evaluated doses i for which $\text{Pr}(\delta_i > 0.25 | \text{data}) < 0.80$.

The RP2D(s) will be selected from dose level(s) at or below the MTD. Additional dose levels may be studied if the MTD(s) have not been reached and pharmacodynamic activity is deemed to be inadequate. At the time of completion of the Phase 1 portion of the study an analysis of the data will be performed.

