3.1.5 Definition of Dose-limiting Toxicities

Toxicity will be evaluated according to the National Cancer Institute (NCI) Common Terminology Criteria for AEs (CTCAE) v4.03 toxicity criteria. Dose-limiting toxicities are defined as those events that will require dose modification; therefore, DLT criteria should be referenced throughout the Phase 1 and 2 portions of the study. The DLT evaluation period will be Cycle 1 (Weeks 1 through 4).

For the purposes of dose level escalation and determination of the MTD(s), only DLTs (as defined below) that occur during the first cycle of treatment will be considered in decisions regarding dose level escalation; however, DLTs or other clinically significant toxicities that occur throughout the observation period will be considered when determining the RP2D(s) for use in this trial and in subsequent clinical trials.

During Cycle 1 of the dose escalation portion, if two of the three subjects in a cohort experience the same Grade 2, treatment-related AE, then subsequent increases in dose level will precede in increments less than 100%. If more than one cohort is treated at the same dose level and greater than 67% of subjects treated at that dose level experience the same Grade 2 treatment-related AE, dose level escalation will precede in increments less than 100%. In such a case, specific dose level increments will be decided by the CRC.

Protocol-defined hematologic DLTs include:

- CTCAE Grade 4 neutropenia \geq 7 days;
- CTCAE Grade 3 or 4 neutropenia with fever \geq 38.5°C;
- CTCAE Grade 3 thrombocytopenia with bleeding;
- CTCAE Grade 4 thrombocytopenia \geq 7 days.

Protocol-defined non-hematologic DLTs include:

- Grade \geq 3 vomiting or nausea \geq 14 days despite the use of optimal anti-emetic treatments;
- Grade \geq 3 diarrhea \geq 14 days despite the use of optimal anti-diarrheal treatments which should include infliximab as per institutional guidelines;
- Serum creatinine $>$ 3.0 x ULN;
- AST or ALT $>$ 5 x ULN; in subjects with liver metastasis who entered the study with Grade 2 elevation of AST or ALT, an AST or ALT increase \geq 50% relative to baseline and lasting \geq 1 week;
- Bilirubin \geq 3.0 x ULN;
- Bilirubin \geq 2.0 x ULN with ALT $>$ 3 x ULN in subjects without liver metastases;

Other non-hematologic toxicities of Grade \geq 3, except for the following:

- AEs related to underlying disease;
- CTCAE Grade 3 fatigue $<$ 14 days;
- Alopecia;

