3.1.6 Safety Assessment for Immunologically Related Toxicity

Based on an incidence of Grade 3 or greater immune-mediated AEs associated with use of ipilimumab or pembrolizumab of approximately 12% to 15%, the following safety precautions will be followed. Examples of relevant toxicities include the following: enterocolitis, hepatitis, dermatitis, neuropathy, endocrinopathy, nephritis, pneumonitis, pancreatitis, non-infectious myocarditis, uveitis, and iritis.

During dose level escalation, if any of the following is observed, the CRC will be convened to review all safety findings for all subjects treated in that cohort and all previous cohorts, including those events that occurred beyond Cycle 1, to guide next steps.

If more than one subject experiences a Grade ≥ 3 , immune-related adverse event (irAE) in a cohort of 3 subjects;

If more than two subjects experience a Grade ≥ 3 irAE in cohorts of 6 subjects.

During the Phase 2 portion of the trial, if the incidence of Grade ≥ 3 irAEs observed in Cycle 1 or in subsequent cycles of treatment exceeds 25%, the CRC will be convened to review all safety findings from all subjects treated in the study to guide next steps.

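### With unequal numbers per dose, the Section 3.1.3 MTD rule can favour a lower, less-studied dose: after 0/3 at 4, 8 and 16 mg, 0/6 at 32 mg gives 16 mg but 1/6 gives 32 mg

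*SAP*

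**What the plan says.** SAP Section 3.1.3 sets the MTD by formula. The model is stated as "Using a prior beta(1,1) distribution of the DLT rate δ_i for each dose level i". The choice is then that "the MTD is defined as the highest dose level for which the mean of the posterior distribution of toxicity is closest to 25" percent, restricted to evaluated doses whose posterior probability of a DLT rate above 0.25 is under 0.80. The word highest can only break ties. The data are first-cycle DLTs: "The MTD will be determined from the assessment of DLTs during the first treatment cycle of each cohort (Section 3.1.5").

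Two decisions depend on the result. "The RP2D(s) will be selected from dose level(s) at or below the MTD". Also, "Additional dose levels may be studied if the MTD(s) have not been reached and pharmacodynamic activity is deemed to be inadequate".

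Cohorts of 3 are planned. Three places foresee more subjects at some doses than at others:

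- Section 3.1.5 has a provision that begins "If more than one cohort is treated at the same dose level".
- Section 3.1.6 sets a review trigger for "irAE in cohorts of 6 subjects" during dose escalation.
- Section 3.1.1 states that "supplemental cohorts of up to 5 subjects each may be enrolled with either combination at doses up to and including the MTD".

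**The concern.** An MTD rule should not lower its answer because more subjects took the top dose without a DLT, nor raise it because one of them had a DLT. This rule can do both. The beta(1,1) prior puts a 0/3 dose at a mean of 0.20, close to the target. Further DLT-free subjects pull the mean down and away from 25%, and the rule treats that as a worse fit. With independent doses, nothing carries the reassurance at a higher dose down to a lower one. Choosing the RP2D is part of the Phase 1 primary objective, and the MTD is its upper limit, so a misplaced MTD can exclude a dose that the data support.

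**Working it through.** **Inputs (SAP Sections 3.1.1 and 3.1.3).** Beta(1,1) prior per dose; target 25%; screen Pr(rate > 0.25) < 0.80; doses 4, 8, 16 and 32 mg in the ipilimumab arm, with the pembrolizumab arm starting at 8 mg; cohorts of 3.

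**Plan's own figure.** The SAP prints no worked MTD result. As a check on the method, the same kind of posterior with the beta(0.6, 1.4) prior reproduces Table 3 for 3 to 9 DLTs (7, 10, 13, 17, 20, 24, 27). For 10 DLTs it gives 31 against 29 printed, which has no bearing here.

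**Formula.** With x DLTs in n subjects the posterior is beta(1+x, 1+n−x), with mean (x+1)/(n+2). For x = 0 the screen probability is 0.75^(n+1).

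| x/n | Mean | Distance from 0.25 | Pr(rate > 0.25) |
|---|---|---|---|
| 0/3 | 1/5 = 0.200 | 0.050 | 0.316 |
| 0/4 | 1/6 = 0.167 | 0.083 | 0.237 |
| 0/6 | 1/8 = 0.125 | 0.125 | 0.133 |
| 1/6 | 2/8 = 0.250 | 0 | 0.445 |
| 2/6 | 3/8 = 0.375 | 0.125 | 0.756 |
| 0/8 | 1/10 = 0.100 | 0.150 | 0.075 |
| 1/3 | 2/5 = 0.400 | 0.150 | 0.738 |

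All of these pass the screen.

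**Rule applied after 0/3 at 4, 8 and 16 mg (each at distance 0.050).**

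| Result at 32 mg | MTD by the rule |
|---|---|
| 0/3 | 32 mg (four-way tie, highest taken) |
| 0/4, 0/6 or 0/8 | 16 mg |
| 1/6 | 32 mg |
| 2/6 or 1/3 | 16 mg |

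The pembrolizumab arm behaves the same way: 0/6 at 32 mg gives 16 mg and 1/6 gives 32 mg. With no DLT anywhere and n = 3, 3, 6, 6 across the four doses, the MTD falls to 8 mg. With 0/6 at all four doses it is 32 mg, so the cause is unequal n.

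**How general it is.** Take n from {3, 6, 8} at each of four doses and 0 or 1 DLT at each lower dose: 3^4 × 2^3 = 648 patterns. Changing 0 DLTs to 1 DLT at 32 mg raises the MTD in 306. This is an unweighted count, not a likelihood.

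**Conditional size.** Assume 6 subjects at 32 mg, 3 at each lower dose, 0/3 or 1/3 at those lower doses, and true DLT rates at 4/8/16/32 mg of (a) 5% throughout, (b) 2/5/10/15%, (c) 5/10/15/25%. The probability of no DLT at 32 mg together with a lower MTD is 0.72, 0.36 and 0.16 in the ipilimumab arm, and 0.71, 0.35 and 0.15 in the pembrolizumab arm. Case (a), ipilimumab arm:

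- No DLT in six at 32 mg: 0.95^6 = 0.735.
- 0 or 1 DLT in three at one lower dose: 0.95^3 + 3 × 0.05 × 0.95^2 = 0.857 + 0.135 = 0.993; for three doses, 0.993^3 = 0.978.
- Less the one pattern that still selects 32 mg, 1/3 at all three lower doses: 0.135^3 = 0.002.
- 0.735 × (0.978 − 0.002) = 0.72.

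With 8 subjects at 32 mg the figures are 0.65, 0.26 and 0.09 (ipilimumab) and 0.64, 0.25 and 0.08 (pembrolizumab). These also assume that the MTD is re-derived after a supplemental cohort of 5.

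**The case against.** The strongest reply is that the planned design never meets the problem: with three subjects at every dose, a DLT-free escalation gives 32 mg. That is correct. It is also true that no sentence calls for expanding a DLT-free dose. The Section 3.1.6 reference to six subjects is a trigger for convening the Cohort Review Committee, and the Section 3.1.5 provision is conditional. If a dose were expanded only after a DLT, which the SAP neither states nor excludes, 0/6 could not arise. The conditions for expansion may be in the protocol or the committee's Charter, which are not at hand. Both points limit the reach of the defect without removing it, since the SAP allows unequal numbers and its formula has no safeguard for them.

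Three stronger readings should be resisted:

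- A reader might take 0.72 as the chance that the trial misplaces its MTD. It is conditional on six subjects at 32 mg and three at each lower dose, and the documents give no probability for that allocation. Its flat 5% DLT rate is also the most favourable scenario: Section 3.1.6 puts Grade 3 or higher immune-mediated events with the partner drugs at about 12% to 15%, though not limited to Cycle 1.
- A reader might rely on the eight-subject figures. Supplemental cohorts follow DLT evaluation of all planned doses and are limited to doses up to the MTD, so an MTD already exists when they enrol. Section 3.1.3 says neither that it is then fixed nor that it is re-derived.
- A reader might infer that naming 16 mg closes dose levels above 32 mg. The SAP does not define when the MTD is not reached. Read literally, the formula names an MTD whenever any dose passes the screen, so the sentence on additional levels could hardly ever apply. A DLT-free escalation may well be meant as not reached.

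The committee guides the next cohort's dose, and RP2D selection also weighs later toxicity. That softens the consequence, but the SAP states no power to override the formula.

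**Conclusion.** The concern holds as a minor defect in a pre-specified rule. When doses carry unequal numbers of DLT-evaluable subjects, the rule can pass over a dose with more DLT-free subjects for a lower, less-studied one, and a single DLT can restore the higher dose. The result is exact arithmetic on the stated definition and needs no assumption beyond unequal n. In the main example the cost is one dose level, 16 mg instead of 32 mg, as the upper limit for the RP2D. How often this would happen cannot be derived from the SAP, because it depends on whether a DLT-free dose is expanded. This reversal errs toward a lower dose, and no Phase 2 hypothesis test is altered.

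**What to change.** Add to Section 3.1.3:

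> *An admissible dose whose posterior mean is at or below 25% is not passed over in favour of a lower dose; if the highest evaluated dose is selected with posterior mean below 25%, the MTD is reported as not reached and that dose is the upper bound for the RP2D and supplemental cohorts.*

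After 0/3 at the lower doses, this gives 32 mg for 0/4, 0/6 and 0/8 at 32 mg, keeps 16 mg for 1/3 or 2/6, and removes all 306 reversals. It also defines when the MTD is not reached.

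It has one disclosed cost: 1/6 at 16 mg with 0/3 at 32 mg moves from 16 to 32 mg, on three subjects at the higher dose.

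Weighted isotonic regression of the posterior means (weights equal to DLT-evaluable subjects) is an acceptable alternative but a larger change. It makes the same move (pooled mean (6 × 0.250 + 3 × 0.200)/9 = 0.233). It also takes 0/3, 0/3, 2/6, 0/3 at 4, 8, 16 and 32 mg from 32 down to 8 mg: the pooled mean at 16 and 32 mg is (6 × 0.375 + 3 × 0.200)/9 = 0.317, at distance 0.067 against 0.050 for 8 mg. The SAP would have to state this.

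Either option changes a dose-finding rule and should be aligned with the protocol and the committee's Charter. No extra subjects or data are needed.

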3.1.3.1 Phase 2 Stopping Rules

Additional subjects will be enrolled at the RP2D level(s) established in the Phase 1 portion of the study for a total of approximately 90 to 100 subjects enrolled in the study. DLTs will be continuously monitored throughout the study. Assuming a prior beta (0.6, 1.4) distribution for the overall toxicity rate for a treatment, a Phase 2 arm will terminate if the $\text{Pr}(\delta_t > 0.25 | \text{data}) > 0.80$, where δ_t is the DLT rate attributable to the treatment. The decision rule for terminating due to toxicity is presented in **Table 3**. The method used to produce the decision rule and operating characteristics was designed by Thall (2006).

Table 3: Phase 2 Stopping Boundaries

If there are this many first-cycle DLTs or more	3	4	5	6	7	8	9	10
Stop if this many subjects (or fewer) have begun treatment	7	10	13	17	20	24	27	29

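### The Phase 2 toxicity stopping table departs from the posterior criterion it is meant to express: its last entry should be 31 rather than 29, nothing covers subjects 30 to 60, and its floor of 3 DLTs is unwritten.

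*SAP*

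**What the plan says.** Section 3.1.3.1 of the SAP sets the criterion: "Assuming a prior beta (0.6, 1.4) distribution for the overall toxicity rate for a treatment, a Phase 2 arm will terminate if the" posterior probability that the arm's DLT rate exceeds 0.25 is greater than 0.80. It also says "DLTs will be continuously monitored throughout the study". No minimum or maximum number of subjects or DLTs is attached to either statement.

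The same paragraph continues: "The decision rule for terminating due to toxicity is presented in" Table 3. The table has two rows, "If there are this many first-cycle DLTs or more" (3 to 10) and "Stop if this many subjects (or fewer) have begun treatment" (7, 10, 13, 17, 20, 24, 27, 29). It is presented as the rule itself, and nothing says which form prevails if they differ.

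On arm size, Section 3.1.2 says "Phase 2 will enroll up to 60 subjects treated at the IMO-2125 + ipilimumab RP2D", with at least 21 in the primary and up to 20 in the secondary efficacy population. For the other arm, "enrollment will continue until 21 subjects in the IMO-2125 + pembrolizumab efficacy-evaluable population have been treated".

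**The concern.** Table 3 has no column below 3 DLTs and none that can act once 30 subjects have begun treatment. The sentence has no such limits.

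- If the table governs, the ipilimumab arm has no toxicity stop for subjects 30 to 60, that is, for up to 31 of 60 subjects.
- If the sentence governs, a DLT in an arm's first subject ends that arm, which is unlikely to be intended.

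Neither form can therefore simply be declared controlling. This is a binding safety stop, and those applying it could receive opposite instructions from the same paragraph. The upper gap matters most when the combination is too toxic. The pembrolizumab arm, planned at 21 evaluable subjects, is touched only at the low end.

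**Working it through.** **Inputs** (Section 3.1.3.1): prior beta(0.6, 1.4), toxicity limit 0.25, cut-off 0.80. Maximum arm size 60 (Section 3.1.2). The SAP states no expected DLT rate, so the rates below are assumptions.

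**Formula.** With d DLTs in n subjects the posterior is Beta(0.6 + d, 1.4 + n − d). The boundary for d is the largest n at which Pr(rate > 0.25) > 0.80.

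**Reproducing Table 3, then extending it:**

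| DLTs | 1 | 2 | 3 | 4 | 5 | 6 | 7 | 8 | 9 | 10 |
|---|---|---|---|---|---|---|---|---|---|---|
| Table 3 | – | – | 7 | 10 | 13 | 17 | 20 | 24 | 27 | 29 |
| Criterion | 1 | 4 | 7 | 10 | 13 | 17 | 20 | 24 | 27 | 31 |

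| DLTs | 11 | 12 | 13 | 14 | 15 | 16 | 17 | 18 |
|---|---|---|---|---|---|---|---|---|
| Table 3 | – | – | – | – | – | – | – | – |
| Criterion | 34 | 38 | 41 | 45 | 49 | 52 | 56 | 60 |

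The exact match at 3 to 9 DLTs shows that the prior and cut-off are read as intended.

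**High end.** Posterior probability at 10 DLTs: 0.863 (n = 29), 0.836 (30), 0.807 (31), 0.776 (32). The boundary is 31. The conflict can be reached: 9 DLTs in 29 gives Beta(9.6, 21.4) and 0.756, so neither form stops. A DLT in subject 30 makes 10 in 30, at 0.836. The sentence stops the arm and the table does not.

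Probability of a toxicity stop, by exact recursion with a check after each subject. Both rules start at 3 DLTs, so only the upper part differs:

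| Assumed DLT rate | Table 3 | Criterion, by 41 subjects | Criterion, by 60 subjects | Gap at 60 (points) |
|---|---|---|---|---|
| 15% | 10.9% | 11.2% | 11.3% | 0.4 |
| 20% | 24.7% | 26.4% | 27.7% | 3.0 |
| 25% | 43.5% | 48.1% | 52.5% | 9.0 |
| 30% | 63.3% | 70.4% | 77.3% | 14.0 |
| 35% | 79.7% | 86.8% | 92.6% | 12.9 |

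The Table 3 figure is the same at 41 and 60, because the table cannot stop an arm after subject 29. Of arms still open at that point, the criterion would stop 16% by subject 60 at a 25% rate and 38% at 30%. Checking only after every 3 subjects leaves gaps at 60 of 2.9, 9.6, 15.9 and 15.4 points at rates of 20, 25, 30 and 35%.

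**Low end.** The criterion is met at 1/1 (0.840), 2/2 (0.954), 2/3 (0.893) and 2/4 (0.816), but not at 1/2 (0.709) or 2/5 (0.731). Differences from Table 3 by 21 subjects, at DLT rates of 10, 15 and 20%:

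- Criterion first applied at 2 to 4 subjects: 3.4, 5.3 and 6.2 points.
- Checks after every 3 subjects: 1.9, 3.2 and 4.0 points.
- Criterion first applied at 5 subjects, or each outcome known only after three or more further subjects have begun: zero.
- Criterion applied from the first subject with fully sequential outcomes: 10 to 14 points.

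If the criterion is restricted to 3 or more DLTs, the two forms give identical stopping probabilities through 21 subjects.

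**The case against.** The strongest reply is that a sensible reader would use the table where it has columns and the posterior beyond them, so stopping would not lapse at subject 30. That reading is reasonable but written nowhere. It also leaves open whether the 10-DLT column, which ends at 29, displaces the criterion at 10 in 30 or 10 in 31, and it does not settle the low end.

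The entry of 29 looks like a cap from a table built for about 30 subjects, not a slip in calculation. That is a plausible inference and would explain the discrepancy, but the arm may now go to 60.

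Other oversight continues after subject 29: monthly data review (Section 3.1.4) and a CRC meeting if Grade 3 or higher immune-related events exceed 25% (Section 3.1.6). Both are real safeguards, but neither is a termination rule for DLTs.

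The point on size largely stands. Sixty is a ceiling. Section 3.3 expects about 60 to 70 Phase 2 subjects in all, which leaves 60 − 21 = 39 to 70 − 21 = 49 for ipilimumab, or more if Phase 1 subjects at the RP2D are counted. By 49 subjects the gap is 0.4, 2.4, 6.8 and 10.5 points at rates of 15, 20, 25 and 30%. Rates of 30% or more exceed the 25% target that the RP2D must already have passed in Phase 1, and the arm may also end for futility after 10 subjects.

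It is also fair that the low end is probably a deliberate floor and is nearly unreachable if Phase 1 subjects at the RP2D enter the toxicity count, which the SAP does not state.

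**Conclusion.** The concern holds. Under the SAP's own prior and cut-off, Table 3 is correct at 3 to 9 DLTs, two subjects short at 10, and absent from subject 30 on, where the ipilimumab arm may still be enrolling. The two forms of one binding rule disagree in states that can occur.

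The upper gap ranges from negligible at DLT rates of 15% or less to 9 points at 25% and 14 points at 30%, if the arm reaches 60 subjects. It is smaller for a smaller arm and nil at 29 or fewer. These figures rest on assumed DLT rates, independent outcomes, a check after each subject, and no stop for futility. The low end is minor. The ORR tests and estimates are untouched. The rule should be corrected because it governs safety and the correction costs almost nothing.

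**What to change.** Two edits to Section 3.1.3.1:

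1. Add a clause that the posterior criterion applies only once at least 3 first-cycle DLTs have occurred in the arm.
2. In Table 3, change the 10-DLT entry from 29 to 31 and add, for the ipilimumab arm, 11: 34, 12: 38, 13: 41, 14: 45, 15: 49, 16: 52, 17: 56 and 18: 60. The last column has little practical use, since almost no enrolment is left to stop, but it completes the rule to the arm's maximum.

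If toxicity stopping is meant to end at 29 subjects, state that limit in the sentence instead of extending the table. That choice belongs to the sponsor and the CRC.

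The cost is one clause, one corrected entry and eight columns. Sample size, data collection and the efficacy design do not change.

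### The Phase 2 toxicity boundary in Table 3 departs from the posterior rule it is meant to present (29 printed, 31 computed for 10 DLTs) and ends at 29 subjects, although the ipilimumab arm may reach 60

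*SAP*

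**What the plan says.** Section 3.1.3.1 sets the model for Phase 2 toxicity monitoring: "Assuming a prior beta (0.6, 1.4) distribution for the overall toxicity rate for a treatment". An arm terminates if the posterior probability of a DLT rate above 0.25 is greater than 0.80. The section then points to the table as the working form of that criterion: "The decision rule for terminating due to toxicity is presented in Table 3". Monitoring has no stated end: "DLTs will be continuously monitored throughout the study".

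Table 3 pairs each count of Cycle 1 DLTs with a largest sample size, in a row headed "Stop if this many subjects (or fewer) have begun treatment". The pairs are 3 DLTs with 7 subjects, 4 with 10, 5 with 13, 6 with 17, 7 with 20, 8 with 24, 9 with 27, and 10 with 29.

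Arm sizes are in Section 3.1.2. For ipilimumab: "Phase 2 will enroll up to 60 subjects treated at the IMO-2125 + ipilimumab RP2D". For pembrolizumab, "enrollment will continue until 21 subjects in the IMO-2125 + pembrolizumab efficacy-evaluable population have been treated".

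**The concern.** The table is presented as the implementation of the posterior criterion, so the two should agree at every sample size an arm can reach. They differ in two ways. The last column does not follow from the stated prior and cut-off. The table also has no entries beyond 29 subjects, less than half of the 60 that the ipilimumab arm may treat.

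People monitoring a trial usually work from the table rather than recompute a beta posterior after each subject. If they do so here, the ipilimumab arm has no tabulated DLT stop from subject 30 on. As an extreme case, 15 DLTs in 30 subjects gives a posterior probability of 0.998 and matches no column of Table 3.

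**Working it through.** **Inputs (SAP Sections 3.1.2 and 3.1.3.1).** Prior beta(0.6, 1.4); DLT-rate threshold 0.25; probability cut-off 0.80; Table 3 as printed; ipilimumab arm up to 60 subjects; continuous monitoring.

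**Formula.** With d DLTs in n subjects the posterior is beta(0.6 + d, 1.4 + n − d). The arm stops if 1 − F(0.25; 0.6 + d, 1.4 + n − d) > 0.80, where F is the beta distribution function. For each d, the table entry should be the largest n that satisfies this.

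**Reproducing Table 3.**

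| DLTs | Printed n | Computed n | Posterior at computed n | Posterior at n + 1 |
|---|---|---|---|---|
| 3 | 7 | 7 | 0.820 | 0.755 |
| 4 | 10 | 10 | 0.829 | 0.776 |
| 5 | 13 | 13 | 0.840 | 0.795 |
| 6 | 17 | 17 | 0.811 | 0.769 |
| 7 | 20 | 20 | 0.826 | 0.789 |
| 8 | 24 | 24 | 0.807 | 0.771 |
| 9 | 27 | 27 | 0.822 | 0.790 |
| 10 | **29** | **31** | 0.807 | 0.776 |

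Seven exact matches confirm the prior, the cut-off and the way of counting. With 10 DLTs the posterior is 0.863 at n = 29, 0.836 at n = 30 and 0.807 at n = 31. The text therefore stops at 10/30 and 10/31, and the table does not.

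Five other priors, beta(1, 1), (0.5, 1.5), (0.5, 0.5), (0.25, 0.75) and (1.4, 0.6), and cut-offs from 0.78 to 0.90 were also tried. None gives the whole printed row. A cut-off of 0.85 gives 29 in the last column but changes the other seven.

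**Extending the rule to 60 subjects.**

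| DLTs | 11 | 12 | 13 | 14 | 15 | 16 | 17 | 18 |
|---|---|---|---|---|---|---|---|---|
| Stop at n or fewer | 34 | 38 | 41 | 45 | 49 | 52 | 56 | 60 |

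**Low end.** The rule is also met by 1 DLT in 1 subject (0.840) and by 2 DLTs in 4 or fewer (0.816 at 2/4). Table 3 starts at 3 DLTs without saying whether that is a deliberate minimum.

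**Effect on the probability of stopping.** This is an exact forward recursion over the DLT count, with a look after each subject. The rule is applied from 3 DLTs on, so the low-end difference plays no part. The table's probabilities do not change after subject 29.

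| True DLT rate | Table 3 | Table 3 with 29 changed to 31 | Rule, N = 41 | Rule, N = 49 | Rule, N = 60 |
|---|---|---|---|---|---|
| 25% | 43.5% | 45.0% | 48.1% | 50.3% | 52.5% |
| 30% | 63.3% | 65.6% | 70.4% | 73.8% | 77.3% |
| 35% | 79.7% | 82.1% | 86.8% | 89.8% | 92.6% |
| 40% | 91% | 92% | 96% | 97% | 98% |

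Up to 29 subjects, table and rule give identical stopping probabilities from 3 DLTs on.

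**The case against.** The strongest reply is that the arm is never without a toxicity rule. The posterior criterion stands in the text with no sample-size limit, monitoring is continuous, and Table 3 only displays the criterion. On that reading the stopping probabilities for the table alone are a worst case. The direct conflict is limited to 10 DLTs at 30 or 31 subjects, and beyond that the table is incomplete rather than contradictory. This stands in part: the text criterion does apply after subject 29. But the SAP calls the table the decision rule, so the text and the tabulated boundary diverge and nothing says which governs.

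The 29/31 error is also small by itself, worth about 2 percentage points at true rates of 30% and 35%. Nearly all of the gap comes from the missing columns. That is correct.

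Sixty is a ceiling. At least 21 primary plus up to 20 secondary ipilimumab subjects makes about 41. The 60 to 70 expected in Phase 2 (Section 3.3), less 21 for pembrolizumab, leaves 39 to 49. At 41 subjects the gap is about half of that at 60, so it is smaller but does not disappear.

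Other safeguards exist: data review at least monthly (Section 3.1.4), and a CRC meeting if Grade 3 or higher irAEs exceed 25% in Phase 2 (Section 3.1.6). These prompt discussion and are not DLT stopping boundaries.

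Finally, the table may have been built for about 30 subjects and not revised. That is plausible, but the SAP states no such limit.

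**Conclusion.** The point holds. One of eight boundary values is wrong under the SAP's own prior and cut-off (29 printed, 31 computed), and the table ends at 29 subjects in an arm that may reach 60. The truncation is the more serious fault. At a true DLT rate of 35%, the chance of never stopping is about 20% by the table, against about 7% by the rule at 60 subjects and 13% at 41.

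These figures assume a look after every subject, a constant DLT rate, stopping from 3 DLTs on, and a monitor who uses the table alone. The coverage gap concerns the ipilimumab arm. The pembrolizumab arm, at 21 evaluable subjects, lies within the table unless more than 29 are treated. The missing entries for 1 and 2 DLTs are secondary and may be intended.

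**What to change.** Make Table 3 and the posterior criterion give the same decision at every sample size up to the planned maximum. If the criterion governs, change 29 to 31 in the 10-DLT column and add columns for 11 to 18 DLTs at 34, 38, 41, 45, 49, 52, 56 and 60 subjects. If monitoring is meant to end near 30 subjects, say so in Section 3.1.3.1 and give the reason. In either case, state whether 3 DLTs is a deliberate minimum, and give the operating characteristics for the boundary finally adopted. Which of the two governs is for the sponsor to decide.

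The cost is one recomputed table and matching wording in the SAP and, where it repeats the rule, the protocol. No extra subjects or procedures are needed.
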